3.2 RANDOMIZATION

After consent and enrollment, participants will be randomly assigned to either low-dose naltrexone or standard-dose nalmefene with a 1:1 allocation ratio using permuted blocks to ensure equal numbers in each arm. Participants and research staff will be blinded to randomization arm.

Study medications will be obtained in St. Petersburg and delivered to the study pharmacist at PSMU prior to initiation of recruitment processes. The study pharmacist will deliver a supply of packaged boxes of study medication labeled with the group assignment to the study team.

Following completion of the baseline assessment, the RA will be directed to the electronic randomization screen in REDCap, which, once submitted, automatically assigns the participant to a randomization group. The RA then retrieves the bottle of study medication from the identified group, labels the bottle with the participant study ID, and enters the group number into REDCap, thus linking the two numbers.

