2.2 STUDY OUTCOMES

Primary Outcomes: The primary outcome for this study is tolerability of medication during treatment. Based on measurements used by other researchers, medication tolerability will be measured via a 0-100 visual analog scale with 0 anchored as “cannot tolerate at all” and 100 as “tolerate perfectly well.” Participants will be asked to estimated tolerability over the previous 2 weeks at each study visit: the primary outcome will be tolerability score at the week 8 visit.

Secondary Outcomes:

- 1) Alcohol reduction measured as a reduction in mean number of grams of pure ethanol consumed per day.
- 2) Treatment discontinuation: defined as patient self-report of stopping medication anytime during the treatment period. Participants will be instructed to notify the study staff in real-time if they discontinue medications, and they will be queried about discontinuation at the week 4 and 8 study visit assessments. Lost-to-follow-up will be assumed to be equivalent to treatment discontinuation.
- 3) Adherence: defined as self-report of the percentage of study medications taken in the past 2 weeks, using a visual analog scale (VAS) from 0 to 100, same as used to assess adherence to HIV medication. Participants will be asked to mark on the ruler what percentage of medication they have taken that week ("0% means no medication, 50% means half your medication, 100% means all your medication"). In addition, medication adherence will be assessed by Riboflavin (50 mg) that will be included in the capsules by the pharmaceutical laboratory. This allows for assessment of medication adherence in both medication arms. Visual inspection of the urine for the presence or absence of riboflavin using ultraviolet (UV) light at the long wave setting (33 nm) in a room with low ambient light will be conducted.
- 4) Reported side effects. We will use a Symptom Checklist based on side effects reported in prior studies of naltrexone, plus an open-ended question to assess for any side effects from study medications in the past 4 weeks at visits 4 and 8. Participants side effects will be rated by trained research assessors, using the Guidelines for Severity Grades (mild, moderate, severe, and life-threatening, death) (See Box 1).
- 5) Medication Satisfaction: This 14-item questionnaire assesses satisfaction with medication to treat chronic conditions and difficulty/inconvenience of use.

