2.3 STUDY DESIGN

This is a randomized, double-blinded, 2-arm study of 16 participants with HIV, chronic pain (defined as any bodily pain of moderate to severe intensity lasting for ≥ 3 months), and past-year heavy alcohol use, defined by NIAAA criteria. The 16 participants will be randomly assigned to either naltrexone or nalmefene with a 1:1 allocation ratio using permuted blocks to ensure equal numbers in each arm. Although we will not be formally testing differences between the naltrexone and nalmefene groups, participants will be randomized to the 2 arms in order to minimize selection bias and confounding in the allocation of interventions. Participants will be treated for 8 weeks, and outcomes (tolerability, alcohol use, side effects, medication adherence and discontinuation, and willingness/desire to continue to take medication at the end of study) will be evaluated at the end of treatment. In addition, we will review changes in pain during treatment with naltrexone and nalmefene to ensure that pain does not get worse and determine whether there is some improvement.

The study design and schedule for study visits and assessments is depicted in Figure 1. After consent and enrollment participants will be randomly assigned to either low-dose naltrexone or standard-dose nalmefene. The schedule of study in-person visits/assessments are as follows: screening visit, baseline, 2, 4, 6, and 8 weeks. At baseline, weeks 4 and 8, full study visits will occur, including assessments of tolerability of medication, medication discontinuation, treatment side effects, self-reported adherence and confirmation of adherence through riboflavin urine testing, self-reported pain, and experimental cold pain tolerance (cold-pressor test). Participants will also be instructed to keep a daily dairy to record pain severity, medication adherence, and alcohol use. Weeks 2 and 6 will be short visits at which time a brief assessment of tolerability, side effects, and adherence will occur. Throughout the course of the study, participants will be expected to come in for three in-person assessments and blood draw visits (screening/baseline, 4- and 8-weeks) and two shorter in-person visits.

Figure 1: Study Design (UH2 Phase)

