If the participant fails the naloxone challenge, s/he will be invited to come back within a week to repeat the challenge. Participants who pass the naloxone challenge will then complete the study assessment, cold-pressor testing and be randomly assigned to either low-dose naltrexone or standard-dose nalmefene. Study medication will be provided by trained physicians, who will instruct participants in proper medication administration and adherence.

Study participants, investigators, staff, and physicians administering the medications will be unaware of specific group assignment.

Participants will be treated for 8 weeks, and outcomes (alcohol reduction, tolerability, side effects, medication adherence and discontinuation, and willingness/desire to continue to take medication at the end of the study) will be evaluated at the end of treatment.

Throughout the course of the study, participants will be expected to come in for five in-person assessments. The schedule of study in-person visits/assessments are as follows: baseline, 2, 4, 6, and 8 weeks. At weeks 4 and 8, full study visits will occur, including assessments of tolerability of medication, reduction in alcohol use, medication discontinuation, treatment side effects, self-reported pain, and experimental cold pain tolerance (cold-pressor test). Participants will also be instructed to keep a daily diary to record pain severity, alcohol use, and medication adherence. Weeks 2 and 6 will be short visits, at which a brief assessment of tolerability, side effects, and adherence will occur.

Visits will be preceded by phone/text reminders to the participant or alternate contacts.

The text message will read: "This is a reminder that your visit to Pavlov Medical University is scheduled for ____ at _____. Please reply to confirm or call [name] to reschedule."

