3.3 INTERVENTION

As of September 18th, 2018, enrollment into arm A of the study was discontinued due to concerns about tolerability of the medication. Enrollment into arm B of the study will continue until we reach the target sample size for this arm (N=8).

Eligible participants will be randomly assigned into one of two study arms: 1) 4.5 mg naltrexone or 2) 18mg nalmefene. Study medication will be provided by trained physicians, who will instruct participants in proper medication administration and adherence.

Drug capsules containing naltrexone hydrochloride (4.5mg) and nalmefene hydrochloride dihydrate (18mg) will be prepared by NonStopPharma, a compounding pharmacy in St. Petersburg, Russia. Doses will look identical; participants and providers will be blinded to assigned medication. Both medication capsules will include Riboflavin. Participants will be instructed to take one capsule orally once per day for 8 weeks. Participants will be given 28 days' worth of medications, with instructions to bring pill bottles/leftover medications to the following visit. Although medication visits will occur every two weeks, providing participants with 28 days of medications will ensure that they will not run out even if they miss the 2 and 6 week visits.

The Food and Drug Administration (FDA) has indicated that an Investigational New Drug (IND) is not needed for studies conducted outside the United States.

3.3.A. NALTREXONE

Participants randomized to this group will receive low-dose naltrexone for 8 weeks.

Participants will be instructed to take the medication once daily for 8 weeks. Naltrexone dosing will start on the day of the baseline visit, after successful passing of the naloxone challenge. If the participant does not pass the naloxone challenge, they will be brought back within a week to try again.

The most common side effects (reported in more than 1 in 10 people) of naltrexone are difficulty sleeping, anxiety, nervousness, abdominal pain/cramps, nausea and/or vomiting, low energy, joint and muscle pain, and headache.

Uncommon side effects (reported in less than 1 in 10 people, but more than 1 in 100 people) of naltrexone are loss of appetite, diarrhea, constipation, increased thirst, increased energy, feeling down, irritability, dizziness, skin rash, delayed ejaculation, decreased potency, and chills.

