Medication inserts will be provided to participants at baseline.

Medication distribution will be as follows:

Naltrexone:

- 28 capsules/bottle

- Participants will receive 1 bottle of 28 capsules at baseline and week 2.

Nalmefene:

- 28 capsules/bottle
- Participants will receive 1 bottle of 28 capsules at baseline and week 2.

Medication bottles will also be labeled. The medication labels will contain the following information:

FOR CLINICAL TRIAL USE ONLY

NALTREXONE/NALMEFENE

STORAGE: Don't store medication above 25°C.

KEEP OUT OF REACH OF CHILDREN AND PETS.

Return all unused medication to the study site.

DATE OF MANUFACTURE:

SHELF LIFE:

3.4.D. LOST OR STOLEN STUDY MEDICATION

If participants report lost or stolen medication, they will be provided with extra study medication. If participants report losing medication more than once, the study team will be alerted and the case discussed to determine a plan of action.

3.4.E. DISCONTINUATION OF STUDY MEDICATION

If as a result of study testing at week 4, a participant is found to have AST/ALT >10x normal, medications will be discontinued and the participants will be appropriately monitored for resolution of the abnormalities. If a participant has AST/ALT >5x normal as a result of study testing at week 4, participant will be rechecked at their 6-week visit to ensure levels do not increase to the threshold of discontinuation. Any participant with symptoms of acute hepatic failure (jaundice, dark urine) will have AST/ALT checked.

Those who discontinue medication will be followed and analyzed by intention to treat.

Participants found to be pregnant during the study will have their study medication discontinued, but will still be followed-up for the duration of the study. Participants who report pregnancy outside of study visits will be instructed to immediately discontinue their study medication and requested to come in for a confirmatory urine pregnancy test.

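### The research assessors who rate side effects handle and record each participant's group code, contrary to the stated staff blind; only the drug behind the code is masked

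*Combined protocol and SAP*

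**What the plan says.** Section 2.3 describes the design: "This is a randomized, double-blinded, 2-arm study of 16 participants with HIV". Section 3.1 says: "Study participants, investigators, staff, and physicians administering the medications will be unaware of specific group assignment". Section 3.2 repeats that participants and research staff are masked to arm.

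Section 3.2 then sets out the supply chain. "The study pharmacist will deliver a supply of packaged boxes of study medication labeled with the group assignment to the study team". After REDCap assigns a group, "The RA then retrieves the bottle of study medication from the identified group", puts the participant's study ID on it and enters the group number in REDCap.

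The RA is the research assessor (section 2.6). Section 2.2 says: "Participants side effects will be rated by trained research assessors". Under section 6.2 the RA also asks about symptoms at each visit, judges whether an event is new or worse than before, and sets the action taken for mild and moderate events.

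Section 3.3 says that the capsules look alike and that participants and providers are masked to the drug. It also reports that, from 18 September 2018, "enrollment into arm A of the study was discontinued due to concerns about tolerability of the medication", while arm B goes on enrolling to eight. Section 6.5 allows a single participant to be unblinded for urgent medical need. It says nothing about other participants who share the same code.

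**The concern.** A rater who knows the group code is masked to the drug but not to the group. That is weaker than sections 3.1 and 3.2 claim, and it can fail in two ways. First, a code shared by a whole arm is broken for that arm, and for the other by elimination, once one participant's drug is known. Second, if something is learned about a group, the rater can attach it to individual participants without knowing the drug. The closure of arm A is such a fact.

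Grading a symptom, asking about it and deciding whether it has worsened all involve judgement. Section 2.7.A lets a higher than expected rate of side effects count against going on to the next phase, and section 8.1 reports the percentage with severe or life-threatening side effects. An expectation held by the rater could therefore reach the decision that this study exists to inform.

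**Working it through.** No stated figure needs to be reproduced. The check traces the code through the plan and then counts how far one code break reaches.

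**1. Who knows the code**
- Claimed in 3.1 and 3.2: staff do not know the group, and research staff are masked to arm.
- Procedure in 3.2: group-labelled boxes go to the study team. The RA is shown the group by REDCap, draws from it and records its number.
- Later supply in 3.4.C, 3.4.D and 3.5: a second bottle at week 2, and extra medication if some is lost. Under group-coded supply each of these needs the group again.
- Rating in 2.2 and 6.2: the same role grades side effects.

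The claim and the procedure cannot both hold. What can hold is the narrower statement in 3.3, that the drug is masked.

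**2. Reach of one code break**

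Inputs: 16 participants in two arms (2.3), allocated 1:1 (3.2), so 8 per arm. The number of codes per arm, m, is not given, so it is varied as an assumption. Codes are taken as evenly spread and, for m of 2 or more, as not showing which of them share an arm.

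Participants whose drug becomes known to someone who holds all the codes and learns one result:
- m = 1: 8 on that code, plus 8 by elimination = 16 of 16
- m = 2: 8/2 = 4 of 16
- m = 4: 8/4 = 2 of 16
- m = 8 (a unique number for each participant): 8/8 = 1 of 16

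Two arms called A and B, and a single group number entered for each participant, point to m = 1.

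**3. Effect of the closure on that count**

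The number in arm A at closure, a, is not given. The final total is 8 + a. With one code per arm, one break therefore reaches at most 8 + a participants, for example 9 if a = 1 and 16 if a = 8.

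Unique numbers do not help entrants after closure, who are all in arm B. If b participants were in arm B at closure (also not given), unblinding one later entrant gives the drug for all 8 − b of them, whatever is on the bottle.

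**4. What the closure itself discloses**
- To an RA who holds the codes: which participants still in follow-up are in arm A, that tolerability concerns led to its closure, and that every later entrant is in arm B.
- Drug identity: 0 of 16 with certainty. Section 3.3 lists the drugs as 1 and 2 and never maps them to A and B.

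**5. Which outcomes are exposed**
- RA-graded side effects: directly.
- Week 8 tolerability, the primary outcome: scored by the participant (2.2). The RA administers the assessment and may help to resolve conflicting answers (4.5), which is a weaker route.
- Comparison of arms: no formal test is planned (2.3, 2.7.A, 8.1).

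**The case against.** The strongest reply is that a masked group code is compatible with a double-blind trial. Section 3.3 defines what is masked as the drug, and the capsules are identical. Section 3.2 puts the group label on the boxes, and the bottle label text in 3.4.C names both drugs and lists no group code. Nothing shows that participants learn their code. Section 6.5 does not say that an unblinding result goes to the RAs. Severity is graded against published criteria, the primary outcome is self-reported and no between-arm test is planned.

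All of this stands, and it limits the size of the problem. It does not reconcile 3.1 and 3.2 with the RA's role, because the RA learns the group from REDCap and the box whatever is printed on the bottle.

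A reader might infer more than the documents support:
- **That closing arm A unblinds everyone.** It discloses arm membership and a tolerability concern, not a drug.
- **That participants are unblinded by the package insert.** Section 3.4.C says "Medication inserts will be provided to participants at baseline" but does not say that inserts differ by arm. Silence is not evidence that they do.
- **That visible codes make allocation predictable.** Section 3.2 allocates "with a 1:1 allocation ratio using permuted blocks to ensure equal numbers in each arm", but certain prediction needs the block size, which is not given. Once only arm B enrols the question no longer arises.

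**Conclusion.** The concern holds in limited form. The statements in 3.1 and 3.2 that staff do not know the group are contradicted by the supply and recording procedure in 3.2, and the staff concerned are those who grade side effects. The drug remains masked until a code is broken.

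If there is one code per arm, a single unblinding can identify the drug for up to 16 of 16 participants (8 + a, given the closure). Unique numbers would limit this to 1 of 16 among participants randomized while both arms were open. This rests on three assumptions: one code per arm is inferred, the person who learns the result must also hold the codes, and the label on the box is taken to be a code. If the box instead showed the drug name, which the text does not exclude, the raters would not be masked to the drug at all.

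The closure adds a risk of biased elicitation and grading for arm A participants still in follow-up. The documents give no basis for estimating how large that bias would be. The consequence falls mainly on the side-effect results and on their part in the decision about the next phase. The primary score is much less exposed.

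**What to change.** In section 3.2:
- Have the pharmacist label each bottle with a unique number that carries no group code, and have REDCap return a bottle number instead of a group.
- Keep the link from number to group with the pharmacist only.
- Remove the group number from every REDCap field that an RA can see.
- Supply week 2 and replacement medication as numbered bottles in the same way.

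Relabelling cannot hide the arm of anyone who entered after 18 September 2018, and it cannot undo ratings made while the group code was known. For both, report the side-effect grades as made by raters who knew the group code but were masked to the drug. Correct the blinding statements in 3.1 and 3.2 to say the same.

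The cost is small. At two bottles per participant the upper limit is 16 × 2 = 32 labels plus spares, and fewer now that arm A is closed. REDCap's allocation table and form need an edit. The pharmacist has slightly more bookkeeping, chiefly for replacement bottles. No extra staff or visits are needed.

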3.3 INTERVENTION

As of September 18th, 2018, enrollment into arm A of the study was discontinued due to concerns about tolerability of the medication. Enrollment into arm B of the study will continue until we reach the target sample size for this arm (N=8).

Eligible participants will be randomly assigned into one of two study arms: 1) 4.5 mg naltrexone or 2) 18mg nalmefene. Study medication will be provided by trained physicians, who will instruct participants in proper medication administration and adherence.

Drug capsules containing naltrexone hydrochloride (4.5mg) and nalmefene hydrochloride dihydrate (18mg) will be prepared by NonStopPharma, a compounding pharmacy in St. Petersburg, Russia. Doses will look identical; participants and providers will be blinded to assigned medication. Both medication capsules will include Riboflavin. Participants will be instructed to take one capsule orally once per day for 8 weeks. Participants will be given 28 days' worth of medications, with instructions to bring pill bottles/leftover medications to the following visit. Although medication visits will occur every two weeks, providing participants with 28 days of medications will ensure that they will not run out even if they miss the 2 and 6 week visits.

The Food and Drug Administration (FDA) has indicated that an Investigational New Drug (IND) is not needed for studies conducted outside the United States.

3.3.A. NALTREXONE

Participants randomized to this group will receive low-dose naltrexone for 8 weeks.

Participants will be instructed to take the medication once daily for 8 weeks. Naltrexone dosing will start on the day of the baseline visit, after successful passing of the naloxone challenge. If the participant does not pass the naloxone challenge, they will be brought back within a week to try again.

The most common side effects (reported in more than 1 in 10 people) of naltrexone are difficulty sleeping, anxiety, nervousness, abdominal pain/cramps, nausea and/or vomiting, low energy, joint and muscle pain, and headache.

Uncommon side effects (reported in less than 1 in 10 people, but more than 1 in 100 people) of naltrexone are loss of appetite, diarrhea, constipation, increased thirst, increased energy, feeling down, irritability, dizziness, skin rash, delayed ejaculation, decreased potency, and chills.

Rare side effects (reported in less than 1 in 100 people) of naltrexone include nasal congestion, itching, rhinorrhea, sneezing, sore throat, excess mucus or phlegm, sinus trouble, heavy breathing, hoarseness, cough, shortness of breath, nose bleeds, phlebitis, edema, increased blood pressure, non-specific ECG

changes, palpitations, tachycardia, excessive gas, hemorrhoids, diarrhea, ulcer, painful shoulders, legs or knees; tremors, twitching, increased frequency of, or discomfort during, urination; increased or decreased sexual interest, oily skin, pruritus, acne, athlete's foot, cold sores, alopecia, depression, paranoia, fatigue, restlessness, confusion, disorientation, hallucinations, nightmares, bad dreams, eyes-blurred, burning, light sensitive, swollen, aching, strained; ears—"clogged," aching, tinnitus, Increased appetite, weight loss, weight gain, yawning, somnolence, fever, and dry mouth,

Please note that these side effects were reported among people taking 50mg of naltrexone. This study will use low dose naltrexone (4.5mg) and side effects are expected to be milder. In order to help prevent these adverse effects, participants will be instructed not to take more medication than what is provided by the study. Study clinicians will also be monitoring for signs of naltrexone overdose. These adverse effects are not expected to be likely.

3.3.B. NALMEFENE

Participants randomized to this group will receive nalmefene for 8 weeks.

Participants will be instructed to take the medication once daily for 8 weeks. Nalmefene dosing will start on the day of the baseline visit after successful passing of the naloxone challenge. If the participant does not pass the naloxone challenge, they will be brought back within a week to try again.

Very common side effects (reported in more than 1 in 10 people) of nalmefene are feeling sick, dizziness, insomnia, and headache.

Common side effects (reported in less than 1 in 10 people, but more than 1 in 100) of nalmefene include loss of appetite, difficulty sleeping, confusion, feeling restless, reduced sex drive, drowsiness, body twitches, feeling less alert, peculiar sensations in the skin like pins and needles, reduced sense of touch, racing heart, a sensation of rapid, forceful, or irregular beating of the heart, vomiting, dry mouth, excessive sweating, muscle spasms, feeling of exhaustion, weakness, discomfort or uneasiness, feeling strange, and weight loss.

Rare side effects of nalmefene (frequency of side effects cannot be estimated from available data) include seeing, hearing or sensing things that are not there and feeling detached from oneself.

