2.7 RECRUITMENT GOALS

We aim to randomize 16 participants into the trial and a total of up to 30 may be enrolled, but not randomized due to not meeting study entry criteria. Existing Russia ARCH (H-31200) participants will be offered to be screened for PETER PAIN. We will also screen St PETER (H-35288) participants at their final St PETER study visit for eligibility. Recruitment beyond PSMU will occur at local NGOs and Russia ARCH network hospitals including the major clinical HIV hospitals (Botkin Infectious Disease Hospital, Leningrad Regional AIDS Center, St. Petersburg City AIDS Center) and addiction hospitals (Leningrad Regional Center for Addictions, St. Petersburg City Addiction Hospital).

2.7.A. SAMPLE SIZE CALCULATION AND POWER

The goal of this study is to assess the feasibility, tolerability and safety of low-dose naltrexone and standard-dose nalmefene to inform a larger pilot RCT. The study will not be powered to detect statistically significant differences in outcomes and formal statistical testing will not be conducted. If we detect substantial intolerance to medication (mean tolerability rated < 80), and/or if other results qualitatively suggest intolerance (i.e. we have a larger than expected percentage who report discontinuation, non-adherence, side effects, and that they would not want to continue meds), we will not proceed to the next phase (UH3). To illustrate the limits of this phase of study, we provide the width of the CIs for the tolerability outcome within each treatment group. We expect < 15% loss to follow-up at 8 weeks and assume 7 evaluable subjects in each arm. Younger et al. observed a standard deviation of 15.1 for tolerability score. Assuming a similar standard deviation for each arm of this study, the length of a 95% confidence interval for mean tolerability would be approximately 22.4 (e.g., if mean tolerability were 80, the 95% CI would span from 68.8 to 91.2) for either arm.

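### Section 3.3 closes arm A and fills arm B alone, but the size, allocation, precision and cross-arm text still describes 16 participants randomised 1:1

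*Combined protocol and SAP*

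**What the plan says.** Section 3.3 opens with a dated notice: "As of September 18th, 2018, enrollment into arm A of the study was discontinued due to concerns about tolerability of the medication". It continues: "Enrollment into arm B of the study will continue until we reach the target sample size for this arm (N=8"). The paragraph directly after it says: "Eligible participants will be randomly assigned into one of two study arms".

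Other current sections read as if nothing had been closed:

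- Section 2.3: "This is a randomized, double-blinded, 2-arm study of 16 participants with HIV", with 1:1 allocation in permuted blocks. The reason given is that "participants will be randomized to the 2 arms in order to minimize selection bias and confounding in the allocation of interventions".
- Section 2.7: "We aim to randomize 16 participants into the trial". Section 3.1 repeats the 16 and random assignment to either drug. Section 3.2 repeats the 1:1 ratio.
- Section 2.7.A: "We expect < 15% loss to follow-up at 8 weeks and assume 7 evaluable subjects in each arm". With an SD of 15.1 it gives a 95% CI length of about 22.4 (68.8 to 91.2 at a mean of 80), stated for either arm.
- Section 8: an intention-to-treat analysis by randomised arm, with descriptive statistics at baseline and each follow-up used to look for apparent differences between the arms.
- Section 8.1: mean tolerability at 8 weeks with a 95% CI within each group, and no formal testing.

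No section gives arm A's number at closure, a revised total, the way participants are assigned after closure, or how later arm B entrants are to be shown.

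**The concern.** After 18 September 2018 the closure notice and the two-arm text cannot both govern enrolment. Three things follow.

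First, the planned total of 16 and the equal arms no longer describe the trial.

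Second, the precision quoted for arm A rests on an arm of 8 with 7 evaluable, and that is no longer planned.

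Third, participants who enter arm B after closure could not have been assigned to arm A. Section 2.3 randomises in order to guard against selection bias and confounding, and that protection does not reach them. Section 8, followed literally, would set arm A beside a mixture of concurrently randomised and later single-arm participants and present them all as randomised. Any difference in who was recruited, or how, before and after closure could then look like a difference between the drugs.

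**Working it through.** **Inputs.** Closure of arm A and arm B target of 8: Section 3.3. Total of 16: Sections 2.3, 2.7 and 3.1. SD 15.1, loss below 15%, 7 evaluable per arm, CI length 22.4: Section 2.7.A. Arm A's number at closure: not given.

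**1. The plan's own figure.** Length = 2 × 1.96 × SD / √n = 2 × 1.96 × 15.1 / √7 = 22.37. The half-length is 11.19, so at a mean of 80 the interval is 68.8 to 91.2. This reproduces Section 2.7.A. The 7 evaluable also follows: 8 × 0.85 = 6.8, about 7.

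**2. The total.** Stopping enrolment into arm A implies that it had fewer than 8. With n_A in arm A and 8 in arm B, the total is n_A + 8, at most 7 + 8 = 15.

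**3. Arm B entrants without a random alternative.** Continuing arm B until it reaches 8 implies that it too had fewer than 8 at closure. If it then reaches 8, at least one participant enters after closure. The exact number is not given. As an illustration only, if the arms were balanced at closure, 8 − n_A of the arm B participants would be later entrants: 4 of 8 if n_A = 4.

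**4. Precision after closure.** Arm B at 7 evaluable is unchanged at 22.4. For arm A, by the same formula and SD and with assumed numbers evaluable:

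| Evaluable in arm A (assumed) | CI length | Interval at a mean of 80 | Against 22.37 |
|---|---|---|---|
| 7 | 22.4 | 68.8 to 91.2 | same |
| 6 | 24.2 | 67.9 to 92.1 | 8% longer |
| 4 | 29.6 | 65.2 to 94.8 | 32% longer |

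If arm A had 7 participants, a 15% loss would leave 7 × 0.85 = 5.95, about 6. With no loss it would keep 7, and 22.4 would still apply.

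**5. What Section 8 does with this.** Its cross-arm description takes everyone by randomised arm and makes no distinction by date. Section 8.1 estimates each arm separately, so its means and intervals do not rely on randomisation.

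**The case against.** The strongest reply is that no planned result or decision changes. Sections 2.3, 2.7.A and 8.1 rule out formal testing, and Section 8 puts the main focus within each group. The rule for moving to the next phase uses a level of tolerability (a mean below 80) with qualitative signals, not a difference between arms. Section 2.7.A offers 22.4 only as an illustration, and Section 8.1 will report each arm's actual interval anyway. The closure notice is dated and clear, so staff are unlikely to go on enrolling to arm A or to 16. Consent times and group numbers are held in REDCap (Sections 4.3 and 3.2), so later entrants can be identified.

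Most of this stands, and it keeps the point modest. It does not remove it. Section 8 itself plans to look for differences between the arms, and being able to identify later entrants is not an instruction to separate or label them. The stated total, the allocation rule and arm A's planning figure also remain at odds with Section 3.3.

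**Conclusion.** The point holds as a conflict within current text, with one consequence for the analysis. The total is at most 15, not 16. At least one arm B participant lacks a random alternative. The 7-evaluable and 22.4 figures are supported for arm B only. This rests on reading Section 3.3 to mean that both arms were below 8 at closure and that arm B goes on to reach 8.

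A reader might infer more than the documents support:

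- **That 22.4 is miscalculated.** It reproduces exactly.
- **That arm A's precision is known to be worse.** Its number is not given, so the lengths of 24.2 and 29.6 are illustrations.
- **That much of arm B is non-concurrent.** Only at least one can be inferred.
- **That the within-arm results or the go/no-go rule are undermined.** Neither depends on randomisation between arms.
- **That closure breaks the blind.** Section 3.2 has the research assessor handling group-labelled stock from the start. Section 3.3 does not say which drug is arm A, so drug identity may stay masked.

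The plan should be corrected, but the harm is limited to the descriptive cross-arm reading and to planning statements that no longer match the design.

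**What to change.** 1. **Sections 2.3, 2.7 and 3.1:** keep 16 as the target set before closure, and add the closure and the revised total (arm A's actual number plus 8 in arm B).
2. **Section 2.7.A:** limit the 7-evaluable and 22.4 figures to arm B, and give arm A's precision at its actual number.
3. **Sections 2.3, 3.1, 3.2 and 3.3:** limit the 1:1 randomisation statement to the period before closure, and say that later entrants are assigned to arm B only.
4. **Section 8:** flag each arm B participant as entering before or after closure. The flag should follow the date of assignment, because the baseline visit may come up to 28 days after screening (Section 3.5.A). Report arm B overall for the within-arm results. For the cross-arm description, either restrict it to participants randomised while both arms were open, or keep everyone and label the display as not fully randomised.

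The cost is amendment text and one flag in the tables, with no additional participants and no new assessments. A restricted display uses fewer arm B participants. The labelled display keeps them all, but the comparison remains not fully randomised.
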